## Synopsis

Sponsor	Univ. [name]. [name] Department of Dental Medicine and Oral Health, Division of Oral Medicine and Orthodontics Medical University of Graz
Title	Revascularization of autotransplanted adult teeth – retrospective analysis of a novel technique
Population	Patients who experienced autotransplantation of adult teeth
Study design	Retrospective data analysis
Objectives	Evaluation of the success rate of reperfusion of autotransplanted adult teeth
Outcome variables	Primary outcome variable: Reperfusion of the transplanted tooth Secondary outcome variable: Periodontal healing
Participants	17 -20 patients
Timetable	Retrospective analysis and data evaluation over 1 month
Inclusion criteria	
 
• Patients who experienced one or multiple autotransplantations of teeth
 
• At least one year of follow-up
 

Exclusion criteria	
 
• Immature teeth with open apices
 
• Different surgical technique
 

## 1. Introduction

Autotransplantation of immature teeth is a routine procedure. It has a high success rate regarding periodontal and pulpal healing. Disruption of blood supply in teeth removed from their socket leads to pulp tissue infarct and coagulation necrosis. (Adreasen and Kahler JOE 2015) After transplantation, there is a good chance of revascularization of necrotic pulp tissue in immature teeth with open apices. However, this outcome is not only threatened by the possibility of infection-related inflammatory root resorption, but the apical pulp canal diameter also seems to play an essential role. The chance of revascularization is significantly diminished in mature teeth with an apical constriction.

Consequently, it is recommended to start root canal treatment of adult transplanted teeth within 7 to 10 days.

[name] et al. (2018) already reported on a unique case, where combining transplantation with a resection of the root tip lead to successful revascularization in a mature tooth

## 2. Methods:

By a retrospective study design, clinical and radiological data regarding patients who experienced tooth transplantation with concomitant root tip resection between July 2017 and June 2020 will be obtained and analyzed. Clinical and radiological findings will be evaluated regarding periodontal and pulpal healing.

## 3. Risk and benefits

It is a retrospective data analysis. There is no risk to patients.

## 4. Objectives and hypotheses of the study

### a) Objectives

To investigate the rate of successful reperfusion of autotransplanted adult teeth.

**b) Hypothesis**

Simultaneous resection of the root tip leads to a higher rate of reperfusion.

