**Exclusion criteria**

- Immature teeth with open apices
- Different surgical technique

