## 6. Statistical considerations

Andreasen et al. determined in their long-term study over 370 transplanted premolars that with completed root growth (and consequently closed foramen apical) only in 60% of cases does periodontal healing occur, while this is to be expected in immature teeth in 90% of cases.

If one compares the pulpal healing in teeth with completed and non-completed root growth, one even comes to a difference of 15 to 96%.

Since this is a retrospective data analysis, the statistical evaluation is carried out by means of descriptive statistics. The result is then compared with published success rates in the subject-specific literature. (Chi square test) It should be shown that the success rate of transplantation of teeth with completed root growth according to the presented method

does not differ from the success rate of transplanted immature teeth with open foramen apical.

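### The hypothesis claims a higher reperfusion rate without naming a comparator, while the statistics section aims to show no difference from immature teeth by a chi-square test without a margin

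*Protocol*

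**What the plan says.** Section 4b of the protocol gives the hypothesis: "Simultaneous resection of the root tip leads to a higher rate of reperfusion". No reference group or rate follows. The Introduction points to one by saying that "The chance of revascularization is significantly diminished in mature teeth with an apical constriction", which suggests mature teeth transplanted without resection.

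No such teeth will be in the data. Section 2 collects "patients who experienced tooth transplantation with concomitant root tip resection", and the exclusion criteria list "Different surgical technique". Any comparator must therefore be external.

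Section 6 plans descriptive statistics and then a comparison by chi-square test: "The result is then compared with published success rates in the subject-specific literature". For pulpal healing with completed against non-completed root growth it says that "one even comes to a difference of 15 to 96" percent; for periodontal healing it quotes 60% and 90%. The one result it sets out to demonstrate is that mature teeth treated with the new technique have a success rate which "does not differ from the success rate of transplanted immature teeth with open foramen apical". It gives no margin and does not say whether success means reperfusion (the primary outcome) or periodontal healing (a secondary one). The Synopsis gives 17 to 20 patients.

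**The concern.** The protocol makes two claims of different kinds. Section 4b is a superiority claim over an unnamed rate, most naturally the low rate in mature teeth. Section 6 is a claim of sameness with the high rate in immature teeth. Three things follow.

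- The plan commits to no test of its own hypothesis. The 15% benchmark that would serve is quoted but not used.
- The sameness claim would rest on a non-significant chi-square test. In a sample this small, non-significance mostly reflects imprecision.
- For many plausible results the two claims come out differently, and the protocol does not say which one is the study's conclusion.

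**Working it through.** **Inputs from the protocol.** n = 17 to 20 patients (Synopsis); pulpal healing 15% with completed and 96% with non-completed root growth (section 6). The sample size has no stated derivation, so there is no figure of the plan's own to reproduce.

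**Assumptions, not in the protocol.** Reperfusion is taken as pulpal healing. The 15% applies to mature teeth without resection. Both published rates are treated as fixed. Each patient contributes one tooth. The main convention is an equal-tailed exact binomial test with 2.5% per tail, which matches the Clopper-Pearson 95% interval. X is the number of successes.

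**1. Testing 4b against 15%.** Find the smallest c with P(X ≥ c | n, 0.15) ≤ 0.025.

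- n = 17: P(X ≥ 6) = 0.032, P(X ≥ 7) = 0.0083, so c = 7.
- n = 20: P(X ≥ 6) = 0.067, P(X ≥ 7) = 0.0219, so c = 7.
- Power P(X ≥ 7 | n, p) for n = 17 / 20: 83% / 94% at a true 50%, and 96% / 99% at 60%.

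**2. Testing the section 6 aim against 96%.** The result differs significantly if P(X ≤ x | n, 0.96) ≤ 0.025.

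- n = 17: P(X ≤ 13) = 0.0040 and P(X ≤ 14) = 0.0286, so 13 or fewer differ.
- n = 20: P(X ≤ 16) = 0.0074 and P(X ≤ 17) = 0.0439, so 16 or fewer differ.

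With an uncorrected one-sample chi-square, (x − 0.96n)² / (n × 0.96 × 0.04) is compared with 3.84.

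- 14/17: (14 − 16.32)² / 0.6528 = 8.25, significant. 15/17: 2.67, not significant.
- 17/20: (17 − 19.2)² / 0.768 = 6.30, significant. 18/20: 1.88, not significant.

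The chi-square cut-offs are therefore 14/17 and 17/20. Expected failures are only 17 × 0.04 = 0.68 and 20 × 0.04 = 0.80, too few for a reliable approximation.

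**3. Results that support 4b but fail the section 6 aim.** Combining steps 1 and 2: 7–13 of 17, or 7–16 of 20 (upper ends 14 and 17 with chi-square).

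**4. How often each outcome arises.** Probability of differing significantly from 96%:

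| True rate | Exact, n = 17 / 20 | Chi-square, n = 17 / 20 |
|---|---|---|
| 60% | 95% / 98% | 99% / 100% |
| 70% | 80% / 89% | 92% / 96% |
| 80% | 45% / 59% | 69% / 79% |
| 90% | 8% / 13% | 24% / 32% |

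The complement is the probability of passing as not different. At a true 80% it is 1 − 0.451 = 55% (n = 17) and 1 − 0.589 = 41% (n = 20) with the exact test, or 31% and 21% with chi-square.

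**5. What a pass would mean.** Under either test 15/17 and 18/20 pass, with exact 95% intervals of 64–99% and 68–99%. With no failures the lower limit is 0.025^(1/n): 0.805 for 17/17 and 0.832 for 20/20. The smallest non-inferiority margin that could be met is then 0.96 − 0.805 = 0.155 (about 16 points) or 0.96 − 0.832 = 0.128 (about 13 points).

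**The case against.** The strongest reply has four parts.

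- **The comparator can be inferred, and the aims do not conflict.** The Introduction makes mature teeth without resection the natural reading of 4b, and a rate near 96% would satisfy both aims. This is true and limits the point: there is no contradiction. But a comparator that the reader must reconstruct is not a stated hypothesis, and the claims diverge over the wide range in step 3.
- **The published rates may include 15%, and the choice may be left to an analysis plan.** Section 6 does allow such a test. It does not fix one, and the only result that it says should be shown uses the other benchmark. An analysis plan can add test details; it should not have to decide what the hypothesis is.
- **The study is descriptive.** Section 4a only sets out to investigate a rate, and section 6 begins with descriptive statistics. Section 6 nevertheless goes on to add a test and a result to be shown.
- **The probabilities depend on the test.** This stands. The minimum-likelihood two-sided exact test gives p = 0.0286 for 14/17 and 0.0439 for 17/20, so it shares the chi-square cut-offs and the 21–31% pass probability at a true 80%. A two-sample chi-square against a published series would depend on denominators that the protocol does not give. Both sets of figures are therefore shown. 15/17 and 18/20 pass under the equal-tailed exact, minimum-likelihood exact and one-sample chi-square tests alike.

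**Conclusion.** The point holds and should be fixed. The textual defect needs no assumption: 4b names no comparator, section 6 would infer sameness from a test without a margin, and no test of 4b is committed to.

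Its size does depend on the listed assumptions, above all fixed published rates and one tooth per patient; section 5.2 admits patients with several transplanted teeth, and clustering would change the precision. On those assumptions, a sample that is adequate for 4b cannot support sameness with 96% to within 10 points, even with no failures. At a true rate of 70% the study would most likely support 4b and fail the section 6 aim (exact test: 79% at n = 17, 89% at n = 20), with no rule for which is reported as the conclusion. Confidence is high on the wording; the exact probabilities vary with the test.

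**What to change.** 1. In section 4b, name the comparator, for example: the reperfusion rate with simultaneous root tip resection is higher than the published rate for teeth with completed root growth.
2. In section 6, test this with an exact one-sample binomial test against the quoted 15%, stating that reperfusion is taken as pulpal healing. Give an exact 95% confidence interval and allow for several teeth per patient. Because 15% is a historical figure treated as known, add a sensitivity check at benchmarks of 20–30% (an assumed range). Seventeen patients would then need 8 to 10 successes and twenty would need 9 to 11, with power at a true 60% of 91% falling to 64% (n = 17) and 94% falling to 76% (n = 20).
3. Remove the inference of no difference from a non-significant chi-square test. Either report the rate with its exact interval beside the immature-tooth rates (96% pulpal, 90% periodontal), or, if matching immature teeth stays a formal aim, state and justify a non-inferiority margin in advance and judge it by the lower confidence limit.

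The cost is wording in two sections and one exact test with its interval on the same data. The drawback is that with 17 to 20 patients a formal claim of matching immature teeth is possible only with a wide margin.

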**c) Outcome Variables:**

**Primary Outcome:** Reperfusion of transplanted teeth

**Secondary Outcome:** Periodontal Healing, Tooth loss

**5. Synopsis****5.1 Design**

Retrospective data analysis

**5.2 Participants****Inclusion criteria**

- Patients who experienced one or multiple autotransplantations of teeth
- At least one year of follow-up

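### Section 6 applies a chi-square test for independent observations to a rate counted in teeth, although patients with several transplanted teeth are eligible and no rule covers teeth of the same patient

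*Protocol*

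**What the plan says.** The quantity under study is a proportion of teeth. The objective in section 4a is "To investigate the rate of successful reperfusion of autotransplanted adult teeth". The primary outcome is "Reperfusion of the transplanted tooth" in the synopsis and "Reperfusion of transplanted teeth" in section 4c. Section 6 speaks of "the success rate of transplantation of teeth with completed root growth according to the presented method", and the comparison series it cites is itself counted in teeth ("long-term study over 370 transplanted premolars").

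The planned size is given in patients, as "17 -20 patients" in the synopsis, without a number of teeth. Section 5.2 makes eligible "Patients who experienced one or multiple autotransplantations of teeth", with no upper limit and no rule for choosing one tooth. The exclusion "Immature teeth with open apices" is applied to teeth.

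Section 6 provides for descriptive statistics and names one inferential method, a chi-square test against published success rates. Its stated aim is to show no difference from the immature-tooth rate. It gives pulpal healing rates of 15% (completed root growth) and 96% (incomplete), and periodontal healing rates of 60% and 90%. The hypothesis in section 4b is a higher reperfusion rate, with no comparator named. Section 7 says that the data are anonymized and kept in an Excel file.

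**The concern.** Teeth of one patient share age, healing capacity, operator, oral hygiene and often the surgical session, so their outcomes may well be positively correlated. Several teeth then carry less information than the same number from different patients. A chi-square test that counts every tooth as independent uses too small a variance: its p value is too small and an interval built the same way is too narrow. The tooth-level proportion itself is not biased by this.

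The direction depends on the comparison. Against the immature-tooth rate, where the aim is to show no difference, the error makes a false difference more likely and so works against the aim. If the higher-rate hypothesis of section 4b is examined against the 15% quoted for completed root growth, a false difference in the upper direction favours the hypothesis.

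**Working it through.** **No figure to reproduce.** The protocol gives no derivation of the 17 to 20 patients, no number of teeth, no significance level and no correlation. What follows shows a range under assumptions.

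**Inputs from the protocol:** 17 or 20 patients (synopsis); reference rates 96%, 90% and 15% (section 6).

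**Assumptions:** about 25%, 50% or 100% of patients have two teeth and the rest one; ICC 0.1 to 0.5; nominal two-sided 5%; published rate taken as fixed; chi-square with 1 df, critical value 3.84, no continuity correction.

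**Step 1, standard error.** With tooth-weighted mean cluster size m = (sum of squared cluster sizes) / (number of teeth), the design effect is DE = 1 + (m - 1) x ICC, and the correct SE is the naive SE times the square root of DE.

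- Smallest case: 17 patients, 4 with two teeth, 21 teeth. m = (13 x 1 + 4 x 4)/21 = 1.38; DE = 1 + 0.38 x 0.1 = 1.038; SE ratio 1.019.
- Largest case: two teeth each. m = 2; DE = 1 + 1 x 0.5 = 1.50; SE ratio 1.225.

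The correct SE is thus about 2% to 22% larger than the naive one.

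**Step 2, type I error at 96%.** The exact distribution of successes comes from convolving single teeth with exchangeable pairs, for which P(both succeed) = p^2 + ICC x p(1 - p). Rejection probability in %:

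| Patients | With two teeth | Teeth | ICC 0 | 0.1 | 0.3 | 0.5 |
|---|---|---|---|---|---|---|
| 17 | 4 | 21 | 5.0 | 5.3 | 6.0 | 6.6 |
| 17 | 8 | 25 | 7.6 | 8.3 | 9.4 | 10.3 |
| 17 | 17 | 34 | 4.6 | 5.4 | 6.9 | 8.3 |
| 20 | 5 | 25 | 7.6 | 8.0 | 8.8 | 9.5 |
| 20 | 10 | 30 | 3.1 | 3.6 | 4.5 | 5.3 |
| 20 | 20 | 40 | 2.1 | 2.7 | 3.8 | 4.8 |

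The part due to clustering is the rise along each row. The smallest is 0.3 points (21 teeth, ICC 0.1) and the largest 8.3 - 4.6 = 3.7 points (34 teeth, ICC 0.5). The differences between rows at ICC 0 come from discreteness.

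**Step 3, other settings.**

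- Two-sample chi-square against an assumed 100 to 300 published teeth at 96%: rise 0.2 to 2.9 points.
- 90% reference (periodontal healing, a secondary outcome), one-sample: rise 0.3 to 6.5 points.
- More than two teeth in some patients: 14 patients with one, 4 with two, 2 with four (30 teeth). m = (14 + 16 + 32)/30 = 2.07, and at ICC 0.5 DE = 1.53. The simulated error at 96% rises from 3.1% to 6.7%, against 5.3% for 30 teeth with at most two per patient.
- 15% reference, 20 patients with two teeth each: expected successes 40 x 0.15 = 6, variance 40 x 0.15 x 0.85 = 5.1, so the test rejects at 1 or fewer or at 11 or more successes. By the Step 2 method, the chance of 11 or more under the null rises from 3.0% (ICC 0) to 6.2% (ICC 0.5). This is the tail that favours the higher-rate hypothesis.

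**Step 4, one tooth per patient.** m = 1 and DE = 1, so the ICC has no influence. At 96% the plain chi-square rejects at 14 or fewer of 17 (type I error 2.9%) and at 17 or fewer of 20 (4.4%). A two-sided exact binomial test has the same rejection regions.

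**The case against.** The strongest reply is that handling several teeth per patient belongs in a statistical analysis plan, which may exist and is not shown. Tooth-level outcomes in a sample of patients are ordinary in dental research, and section 6 puts descriptive statistics first. The effect may be nil, and discreteness alone moves the level between 2.1% and 7.6% in the table, more than clustering does.

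Much of this stands. A reader might infer that a later plan must abandon the named test. The protocol does not support that: it fixes no variant and no analysis set, so a plan could keep the chi-square on one tooth per patient or use a cluster-adjusted version. A reader might also infer that the type I error must exceed 5%, or that the error always suits the investigators. Neither follows: with 40 teeth the level stays below 5% at 96%, and the direction depends on the comparator.

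What does not stand is that this is only missing detail. The protocol names a test and, in the same document, admits data that can break its independence assumption. Section 6 applied to all teeth as written would treat teeth of one patient as independent.

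**Conclusion.** The point holds as a conditional one: the named test does not fit the data that the inclusion criteria allow, unless each patient contributes one tooth or the grouping is taken into account. Under the assumptions shown, the consequence at the 96% reference is modest, with a correct SE about 2-22% larger and 0.3 to 3.7 points added to the type I error. Teeth per patient, ICC and the 5% level are all assumed, and the cap of two teeth is not the protocol's. The effect vanishes with one tooth per patient and could exceed this range with more than two. The correction is worth making because it is cheap and, in a retrospective study, teeth per patient can be counted from the records.

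The wording in section 7 might be taken to mean that patient identity is lost and grouping impossible. It does not say so: anonymized rows can still carry a patient index. It simply does not say that they will.

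**What to change.** In section 6, state that the tooth is the unit of analysis and the patient the cluster. Report the numbers of patients, of teeth, and of patients with more than one tooth. Base the test and the 95% interval on one of these:

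- a cluster-adjusted chi-square over all teeth, with a patient-level interval (cluster-robust or bootstrap); or
- one pre-specified tooth per patient: the first eligible tooth transplanted or, if several were transplanted in one session, one drawn at random with a fixed seed.

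Take test and interval from the same inversion so that they agree. A two-sided exact binomial test paired with a Clopper-Pearson interval would not: at 14/17 and 17/20 the test rejects 96%, while the upper limits of 96.2% and 96.8% still include it. Label any chi-square over all teeth as ignoring the grouping. In section 7, state that a non-identifying patient index is kept in the file.

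The cost is a few sentences and one column. The one-tooth analysis uses fewer observations: power against a true rate of 80% is 69% (17 patients) or 79% (20), compared with about 80-93% for the unadjusted all-teeth test, whose level is not controlled. Lower power makes non-rejection easier, so non-rejection must not be read as proof of no difference. The cluster-adjusted route keeps all teeth, but robust and bootstrap intervals are unreliable with so few patients and few failures, and a bootstrap interval collapses to a point if no tooth fails. The one-tooth analysis should therefore be named as the fallback.

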**Any known or foreseeable factors that may affect the results of the study or its interpretation:**

- Missing data

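### Requiring one year of follow-up for entry can exclude patients who lost the tooth early, although tooth loss is an outcome

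*Protocol*

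**What the plan says.** Section 5.2 has two inclusion criteria: "Patients who experienced one or multiple autotransplantations of teeth" and "At least one year of follow-up". The Synopsis repeats both. Neither place says whether the year is observed follow-up or time elapsed since surgery, and neither makes an exception for a tooth lost sooner.

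Section 2 draws the source cohort by treatment date: data on patients who had "tooth transplantation with concomitant root tip resection between July 2017 and June 2020 will be obtained and analyzed".

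Section 4c gives the primary outcome as "Reperfusion of transplanted teeth" and the secondary outcomes as "Periodontal Healing, Tooth loss". The Synopsis lists only periodontal healing as secondary.

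After section 5.3, under the heading "Any known or foreseeable factors that may affect the results of the study or its interpretation", the only entry is missing data. Section 6 plans descriptive statistics and a chi-square comparison with published rates. The aim is to show that success with this technique "does not differ from the success rate of transplanted immature teeth with open foramen apical".

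**The concern.** Eligibility should be decidable from what is known at surgery, or from the calendar. Here it depends on what happened afterwards. If a patient's tooth was lost at, say, month four and the patient then stopped attending, the outcome event has itself caused the exclusion. The excluded cases are then enriched for failures.

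Listing missing data as a foreseeable factor does not cover this. A patient screened out on eligibility is not a participant with a missing value, so missing-data methods applied to the analysed set cannot bring that patient back.

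At stake are the tooth-loss rate directly and, if a lost tooth counts as a failure, the success rate. Both would move in the direction that section 6 sets out to show. The planned sample is small enough for a single such patient to be visible in the result.

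**Working it through.** The protocol gives no figure that depends on this rule, so there is nothing to reproduce. The calculation shows how sensitive the planned rates are.

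**Inputs**
- n = 17 or 20 patients (Synopsis).
- Reference rate for pulpal healing in immature teeth: 96% (section 6).
- Assumed: one tooth per patient (section 5.2 allows several), a lost tooth counted as a failure (not stated), and k = 1 or 2 early losses excluded (no count is given).

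**Success rate.** With x successes among n analysed patients, the reported rate is x/n. With the k losses restored it is x/(n+k). The inflation is x/n − x/(n+k).

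| Reported | One loss restored | Inflation, k=1 | Inflation, k=2 |
|---|---|---|---|
| 15/17 = 88.2% | 15/18 = 83.3% | 4.9 points | 9.3 points |
| 18/20 = 90.0% | 18/21 = 85.7% | 4.3 | 8.2 |
| 17/17 = 100% | 17/18 = 94.4% | 5.6 | 10.5 |
| 20/20 = 100% | 20/21 = 95.2% | 4.8 | 9.1 |
| 12/17 = 70.6% | 12/18 = 66.7% | 3.9 | – |
| 10/20 = 50.0% | 10/21 = 47.6% | 2.4 | – |

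**Tooth-loss rate.** With y losses reported, the understatement from one excluded loss is (y+1)/(n+1) − y/n:
- 0/17 = 0% becomes 1/18 = 5.6%: 5.6 points.
- 0/20 = 0% becomes 1/21 = 4.8%: 4.8 points.
- 1/17 = 5.9% becomes 2/18 = 11.1%: 5.2 points.
- 1/20 = 5.0% becomes 2/21 = 9.5%: 4.5 points.

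**Net direction.** The rule can also remove teeth that were doing well but were watched for less than a year. The reported rate is too high whenever the excluded teeth did worse than the included ones. At 18/20, nine excluded successes would be needed to offset each excluded loss: (18+9)/(20+10) = 27/30 = 90%. With one of each excluded, the full-cohort rate is 19/22 = 86.4%, still below the reported 90.0%.

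**Comparison with 96%.** Section 6 names a chi-square test but not its form. The two-sample rows assume a comparator of 96/100.

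| Test | 18/20 | 18/21 |
|---|---|---|
| One-sample chi-square | 0.171 | 0.016 |
| Exact binomial | 0.190 | 0.0497 |
| Two-sample chi-square | 0.261 | 0.066 |
| Same, continuity-corrected | 0.574 | 0.186 |
| Fisher exact | 0.261 | 0.0996 |

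For the one-sample chi-square at 18/21, the expected counts are 20.16 and 0.84, so the statistic is 2.16²/20.16 + 2.16²/0.84 = 5.79. An expected count of 0.84 makes that p-value unreliable. One restored loss crosses 5% under the two one-sample tests and not under the others, so I draw no conclusion about significance.

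**The case against.** The strongest reply is that the defect is an undefined term and not a wrong rule. If follow-up means time since surgery, no early loss is excluded, and an analysis plan that is not shown could say so. That is correct about the consequence. However, follow-up ordinarily means observation, and the two readings select different patients. The criterion belongs to the protocol and should be settled before charts are selected.

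The harm also needs several things at once: a tooth lost within the year, that patient ceasing to attend (the rule is per patient, so someone who keeps attending still qualifies) and, for the success rate, a lost tooth counted as a failure. All of this stands. It limits the claim to possible exclusion of early tooth loss. Failed reperfusion alone need not end follow-up, since the Introduction notes for adult teeth that "it is recommended to start root canal treatment of adult transplanted teeth within 7 to 10 days".

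A minimum follow-up has a sound purpose, because healing cannot be judged too early. That justifies a year between surgery and data extraction. It does not justify a year of observation for a tooth whose outcome is already known.

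The clear conflict is with a secondary outcome, and a shift of 2 to 6 points matters little against the 15% that section 6 cites for mature teeth. That is fair. It matters for the comparison with immature teeth, which is the aim section 6 states.

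**Conclusion.** The concern holds and should be fixed. On the ordinary reading, the inclusion rule allows an outcome event to remove a patient from a cohort otherwise defined by treatment date, and nothing else in the protocol prevents it. Under the stated assumptions, each excluded early loss inflates success by 4.3 to 5.6 points at reported rates of 88 to 100%, and by 2.4 to 3.9 points at 50 to 71%. Two excluded losses add 8.2 to 10.5 points at 88 to 100%. Tooth loss is understated by 4.5 to 5.6 points per excluded loss, however reperfusion is coded.

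The actual size is unknown. It is zero if no patient left follow-up after an early loss, or if the year is counted from surgery. A report following the current wording would not let readers tell which case applies.

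**What to change.** Reword the criterion in section 5.2 and the Synopsis so that eligibility rests on dates: every patient treated with this technique between July 2017 and June 2020 whose surgery was at least one year before data extraction, whatever the observed follow-up.

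State how each tooth is then counted:
- A tooth lost before one year is a failure.
- Any other tooth is classified by its status at one year or later.
- A tooth with no one-year record and no documented loss stays in the denominator as indeterminate, and the rate is given with that tooth counted first as a failure and then as a success.

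This stops selective removal in both directions. With one early loss and one indeterminate tooth, 18/20 = 90.0% becomes 18/22 = 81.8% to 19/22 = 86.4%, and 17/17 = 100% becomes 17/19 = 89.5% to 18/19 = 94.7%. With no early loss and one indeterminate tooth, 18/20 becomes 18/21 = 85.7% to 19/21 = 90.5%, a range that contains the reported 90.0%.

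The cost is one reworded criterion and a few more charts from the same archive. The success rate may come out lower, and each indeterminate tooth widens the range by about 4.5 points (1/22) to 5.3 points (1/19) in these examples.
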